3.2. Statistical Analysis Issues

3.2.1. Strata and Covariates

There is no stratification and covariate analysis planned for this study. However, if there is any stratification and covariate analysis performed in an ad hoc exploratory nature, it will be noted in the final CSR.

3.2.2. Examination of Subject Subsets

There is no subgroup analysis planned for this study. However, if there is any subgroup analysis performed in an ad hoc exploratory nature, it will be noted in the final CSR.

3.2.3. Multiple Comparisons

No formal hypothesis testing and no multiple comparisons will be conducted for this study.

3.2.4. Multi-center Studies

The study will be conducted from approximately 15-20 centers in the United States. Randomization to the treatment groups will not be stratified by study site due to small sample size. Subjects from all centers will be pooled for summaries.

3.2.5. Missing Data and Outliers

Every attempt will be made to capture all study data. For subjects whose visit value is missing, the last observation will be carried forward (LOCF) for the efficacy analyses. Any missing, unused, or spurious data will be noted in the final CSR.

3.2.6. Data Conventions and Transformations

Laboratory numeric data may be recorded with a '<' or '>' sign (i.e. < 0.1 or > 0.1). In order to summarize the data, the original value will be converted to 0.09 in the case of < 0.1 and to 0.11 in the case of > 0.1. The same principle will be used if the data has additional extended significant digits. The actual values will be presented in the data listings.

3.2.7. Study Baseline and Study Day

Baseline is defined as the last assessment prior to the first dose of study drug (RSLV-132 or Placebo) at Day 1. Measurements that are obtained after the first dose of study drug will be considered post-baseline values. Change from baseline is defined as post-baseline assessment minus baseline assessment.

Study day for events on or after the date of the first dose will be defined as the number of days from the date of the first dose of study drug, plus 1 day, so that the date of the first dose will be defined as Day 1. For events before the date of the first dose, study day will be calculated as the difference in days between the date of the first dose and the date of interest. Thus, the day before the date of the first dose will be defined as Day -1.

3.2.8. Visit Windows

The case report form nominal visits and visit windows will be used in the summaries. In general, unscheduled visits will not be summarized unless otherwise noted.

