#### **6.4 Subject Withdrawal Criteria**

Subjects will be informed that they are free to withdraw from the study at any time and for any reason. The Investigator may remove a subject from investigational treatment if, in the Investigator's opinion, it is not in the best interest of the subject to continue. Notification of discontinuation of investigational treatment will be made immediately to the Sponsor. In case of premature discontinuation of investigational treatment, efforts will be made to perform all End of Treatment (EOT) assessments and an End of Study (EOS) visit outlined in (Appendix A).

If a subject wishes to withdraw from the study, the site staff should confirm whether the subject is agreeable to continue the assessments without the investigational treatment or if they wish no further involvement in the study. In the latter case no further study-related evaluations will be performed and no additional data will be collected.

The date and the reason for discontinuation of investigational treatment or withdrawal from the study will be recorded on the subject's Case Report Form (CRF). Subjects that withdraw after receiving study drug will not be replaced.

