## 12 STUDY PROCEDURES

### 12.1 Evaluations

Evaluations are summarized in Appendix A. During the course of the study approximately 295 mL of blood will be drawn. A central laboratory will perform all evaluations with the following exceptions:

- anti-drug antibody evaluations will be performed by ICON.
- autoantibody assessments will be performed by the University of Washington Clinical Laboratory.
- measurement of drug concentration by will be performed by ICON.
- measurement of RNase enzyme activity will be conducted by Resolve Therapeutics.
- serum protein analysis will be conducted by Myriad RBM.
- blood-cell gene expression analysis will be performed by Q Solutions.
- Each site will perform a urine pregnancy test on females at the baseline visit only

Every attempt will be made to perform evaluations on the scheduled day and time, as appropriate. If evaluations cannot be performed on the day of the scheduled visit a window of  $\pm$  3 days may be applied for visit Days 8 through 155 and  $\pm$ 5 days for Day 169 and Day 215. In the event visit windows are utilized the minimum interval between administrations of RSLV-132 should be 10 calendar days.

All scheduled study visits should occur on the specified number of days after Baseline, even if a preceding visit occurred off-schedule.

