### 12.5 Procedures on Days 29, 57, 85, 113, 141, and 169/End of Treatment (EOT)

Prior to study drug administration (pre-dose procedures):

- directed physical examination;
- adverse event assessment;
- interim medication history;
- vital signs (temperature, respiratory rate, blood pressure and pulse);

- Chem-20, CBC, UA;
- measurement of SLE activity (SLEDAI-2K, BILAG-2004, PGA);
- measurement of cutaneous disease activity (CLASI);
- tender and swollen joint count;
- photographs of cutaneous disease activity (Days 85 and 169 only);
- FACIT fatigue index (subject completes form) (Days 85 and 169 only);
- serum for study drug concentration (Days 29, 85, and 169 only);
- serum for protein analysis (Day 85 and 169 only);
- serum for RNase activity (Days 29, 85, and 169 only);
- whole blood for gene expression profile (Days 29, 85, and 169 only);
- serum for autoantibody profile (Ro-52/60, La, Sm, SmRNP, U1 RNP A/68, dsDNA) C3 and C4 (local or central laboratory);
- serum for assessment of anti-RSLV-132 antibodies (Days 29 and 85 only);
- **after completion of above assessments:**
  - study drug administration (except Day 169)

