2.3.5. Subject Withdrawal

Subjects will be informed that they are free to withdraw from the study at any time and for any reason. The Investigator may remove a subject from investigational treatment if, in the Investigator's opinion, it is not in the best interest of the subject to continue. Notification of discontinuation of investigational treatment will be made immediately to the Sponsor. In case of premature discontinuation of investigational treatment, efforts will be made to perform all End of Treatment (EOT) assessments and an End of Study (EOS) visit outlined in SAP Section 2.3.3 Table 1.

If a subject wishes to withdraw from the study, the site staff should confirm whether the subject is agreeable to continue the assessments without the investigational treatment or if they wish no further involvement in the study. In the latter case no further study-related evaluations will be performed and no additional data will be collected.

The date and the reason for discontinuation of investigational treatment or withdrawal from the study will be recorded on the subject's Case Report Form (CRF). Subjects that withdraw after receiving study drug will not be replaced.

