9.1. Analysis of Primary Efficacy Endpoints

The primary efficacy endpoints are the improvements from Baseline (Day 1) to Day 85 and Baseline to Day 169 CLASI Activity scores.

CLASI Activity assessment will be performed for each subject at scheduled visits to determine the SLE disease activity for each subject at the visit. The assessment includes each anatomical location. The total score of the Activity subsection (defined as the sum of the scores from each anatomical location) will be used in the summary. The improvements from Baseline (Day 1) to Day 85 and from Baseline (Day 1) to Day 169 in the total activity score will be evaluated as part of the primary efficacy endpoints. Lower score represents less disease activity.

Summary of observed values: Observed values of total Activity score and the change and percent change from baseline at each scheduled visit will be summarized. In addition to the LOCF imputation described below, the primary endpoints (change from Baseline on observed values) will be analyzed using Mixed effect Model Repeat Measurement (MMRM) method. The MMRM model will include the fixed categorical effects of treatment, random effect visit, and treatment-by-visit interaction, as well as continuous fixed covariates of baseline score and baseline score-by-visit interaction. An unstructured covariance structure of random effect will be used for modeling the within-subject errors.

Summary of imputed values: LOCF imputed values and the change and percent change from Baseline (Day 1) in the CLASI Activity total score at Days 85 and 169 and at each scheduled visit will also be analyzed. The two-sample t-test will be used for the treatment group comparison on the change from Baseline.

Summary of non-censored values: Non-censored values and LOCF imputed non-censored values as well as the change and percent change from Baseline (Day 1) in the CLASI Activity total score at Days 85 and 169 and at each scheduled visit will also be analyzed. The two-sample t-test will be used for the treatment group comparison on the change from Baseline. The following values will be censored based on blinded review before database lock:

- a. Values obtained within 60 days of a steroid (systemic/oral/topical but not ophthalmic or inhaled) dose that is increased above baseline for more than one day
- b. Addition of other systemic agents for lupus (such as antimalarials, methotrexate, rituximab, dapsone)

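### An End of Treatment assessment done weeks early can be analysed as an observed Day 169 value, because data are assigned by nominal visit and the only End of Treatment visit in the schedule is Day 169

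*SAP*

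**What the plan says.** - **After early discontinuation.** SAP 2.3.5: "In case of premature discontinuation of investigational treatment, efforts will be made to perform all End of Treatment (EOT) assessments", together with an End of Study visit, as set out in SAP Table 1. Protocol 6.4 says the same and points to Appendix A. Both sections let a subject who stops drug continue with assessments. A subject who wants no further involvement has no further evaluations.
- **The schedule.** Protocol Appendix A and SAP Table 1 each have one EOT column, headed Day 169 (EOT), and none for early termination. Protocol 12.5 also treats Day 169 and EOT as one visit, with CLASI among its procedures.
- **Assignment to visits.** SAP 3.2.8 has two sentences: "The case report form nominal visits and visit windows will be used in the summaries" and "In general, unscheduled visits will not be summarized unless otherwise noted". SAP 3.2.7 defines study day, but nothing links it to visit assignment. The only windows given are for scheduling (protocol 12.1 and the schedule tables): ±3 days for Days 8 to 155, and ± "5 days for Day 169 and Day 215".
- **Analysis.** SAP 9.1 makes the change in CLASI activity to Day 85 and to Day 169 the primary endpoints, and says "the primary endpoints (change from Baseline on observed values) will be analyzed using Mixed effect Model Repeat Measurement (MMRM) method". SAP 3.2.5 adds: "For subjects whose visit value is missing, the last observation will be carried forward (LOCF) for the efficacy analyses". The revision table in SAP 12 records that the repeated-measures analysis was added because missing data bias it less than they bias LOCF.

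**The concern.** The withdrawal rule produces EOT assessments well before Day 169. The assignment rule then looks to the nominal visit, and the only nominal visit called EOT is Day 169. If the CRF follows the schedule, a CLASI score taken on Day 50 after the drug was stopped is recorded as Day 169 and enters the MMRM as an observed value there. The model has no reason to treat it as anything else. For that subject the carry-forward has already happened in the data, so the MMRM cannot deliver the benefit for which it was added.

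SLEDAI-2K, PGA, FACIT-Fatigue and joint count use the same model (SAP 9.2.1, 9.2.3, 9.2.4, 9.2.5) and are exposed in the same way.

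There are two side effects. An EOT done around Day 85 but filed under Day 169 leaves Day 85, the other primary time point, empty, and LOCF for CLASI then reaches back to Day 57. A subject who has an early EOT and later attends the real Day 169 visit off treatment could have two records under one label, and the SAP does not say which to use.

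**Working it through.** The plan has no figure to reproduce. SAP 2.3.7 sets about 50 subjects by precedent, and no effect size, SD or dropout rate is given. The checks below use the schedule where possible and labelled assumptions elsewhere.

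**1. How early an early EOT can be.** Assume it is done at the next scheduled visit after the last dose.
- Last dose Day 15, EOT Day 29: 169 − 29 = 140 days early (20 weeks).
- Last dose Day 71, EOT Day 85: 169 − 85 = 84 days early (12 weeks).
- Last dose Day 141, EOT Day 155: 169 − 155 = 14 days early (2 weeks).

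All three fall outside Days 164 to 174.

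**2. Whether the scheduling windows could place it.** Days 2 to 163 are 162 days. The visits on Days 8 to 155 give 12 windows of 7 days, which is 84 days. So 162 − 84 = 78 days lie in no window, for example Days 145 to 151 and 159 to 163. Used as analysis windows, they would keep an early EOT out of Day 169 but would often leave it unplaced.

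**3. Dilution of a true effect.** Assume the effect grows linearly from Day 1 to Day 169 and a share f of each arm has its EOT on day d, filed as Day 169. The share of the effect retained is (1 − f) + f(d − 1)/168.

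| f | d = 127 | d = 85 | d = 43 |
|---|---|---|---|
| 10% | 0.975 | 0.950 | 0.925 |
| 20% | 0.950 | 0.900 | 0.850 |
| 30% | 0.925 | 0.850 | 0.775 |

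The dilution is therefore 2.5% to 22.5%.

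**4. Spurious difference under no effect.** Assume both arms improve linearly by 6 points to Day 169, with early EOT in 10% of the active arm and 30% of placebo. An EOT on Day 85 falls short by 6 × (1 − 84/168) = 3 points, so active minus placebo is 0.1 × 3 − 0.3 × 3 = −0.6. On Day 43 the shortfall is 6 × (1 − 42/168) = 4.5, giving −0.9. Negative values favour active. With equal dropout the difference is 0.

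**5. Simulation of the MMRM.** The run used 1,500 trials of 33 and 17 subjects, with generalised least squares on visit means, a known covariance and no baseline covariate, as a stand-in for the MMRM. Assumptions: SD 6; placebo improves linearly by 6 points; early EOT on Day 57, 85, 99 or 113 with equal chance; dropout unrelated to outcome; every discontinuer attends an EOT and has no later visit.

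| True difference | Early EOT, active / placebo | MMRM, filed as Day 169 | MMRM, filed by study day | LOCF, either filing |
|---|---|---|---|---|
| −3 | 20% / 20% | −2.67 | −2.95 | −2.67 |
| −3 | 30% / 30% | −2.62 | −3.07 | −2.62 |
| 0 | 10% / 30% | −0.56 | 0.03 | −0.56 |
| 0 | 20% / 20% | −0.01 | 0.00 | −0.01 |

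The standard error of one complete-data trial is √(36/33 + 36/17) = 1.79, so the simulation error is about 1.79/√1500 = 0.05. The formula in step 3 agrees: the mean EOT day is (57 + 85 + 99 + 113)/4 = 88.5, so with f = 20% the retained share is 0.8 + 0.2 × 87.5/168 = 0.904, or −2.71.

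Filed as Day 169, the MMRM estimate equals the LOCF estimate. LOCF itself is the same under either filing, because the early EOT is the last observation anyway.

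**The case against.** The strongest reply is that the rule refers to CRF visits and the CRF is not available. A column in the schedule is not a CRF visit code, and a separate early-termination visit would prevent the mislabelling. This stands as a condition on the whole point. The SAP would still need to say where such a value is analysed.

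Second, SAP 3.2.8 also mentions visit windows. If Days 164 to 174 were enforced, an early EOT could not count as Day 169. That is a possible reading, but the SAP neither states it nor says where the value would go. A reader might infer that the value is then dropped as unscheduled and an older one carried forward. The documents do not say so. An early EOT is a requested assessment, and the LOCF sentence is not limited to scheduled visits.

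Third, the reach is limited. The Day 169 LOCF comparison normally does not move. A reader might infer that the MMRM loses its benefit for every dropout, but subjects who leave entirely have no EOT and stay missing, and those who continue off treatment can supply a true Day 169 value. Only subjects with an early EOT and no real Day 169 visit are clearly affected.

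Fourth, SAP 2.3.7 and 5 plan no formal hypothesis testing and treat p-values as descriptive. That lowers the consequence. The estimate still matters, because protocol section 4 describes a search for clinical activity before a larger phase 2 study.

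**Conclusion.** The point holds, conditional on the CRF. Nothing in the two documents prevents an early EOT from being analysed as observed Day 169 data. The harm falls on the observed-value summaries and the MMRM at Day 169, with a possible loss of a value at Day 85.

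The size cannot be derived from the documents. The 2.5% to 22.5% dilution, and a spurious difference of roughly half a point to one point under 10% versus 30% early EOT, rest on assumed dropout, a linear time course and a 6-point improvement. Against a standard error of about 1.8 points at the assumed SD of 6, a shift of 0.56 is about 0.3 standard errors. It would not dominate the result, but it is systematic and avoidable. With equal dropout and no effect there is essentially no bias. The figures should not be read as a prediction for this trial, nor as showing that the mislabelling will occur.

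**What to change.** Rewrite SAP 3.2.8 to say:

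- Every post-baseline efficacy assessment, including EOT, is assigned by actual study day to contiguous, non-overlapping post-baseline analysis windows, defined for each measure's own schedule. No post-baseline value maps to baseline.
- Only an assessment on Days 164 to 174 counts as Day 169.
- An early EOT is used at the visit whose window contains its study day. If the measure has no such visit, as for FACIT-Fatigue far from Day 85, the value serves only as the last observation for LOCF.
- Day 169 is missing in the observed-value and MMRM analyses only when the subject has no assessment on Days 164 to 174. A genuine off-treatment Day 169 value is kept.
- With two records in one window, use the one closest to the target day, and the later one if tied.

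Mapping to the nearest scheduled visit would not be enough. A FACIT-Fatigue EOT on Day 130 is nearer Day 169 (39 days) than Day 85 (45 days), and one on Day 30 is nearest baseline.

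The cost is a few lines of SAP text, one derivation in the analysis dataset, and fewer observed Day 169 values, including any Day 169 visit held after Day 174. No new data or procedures are needed.

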4. INTERIM ANALYSIS AND DATA MONITORING COMMITTEE

There is no interim analysis and data monitoring committee planned for this study.

5. GENERAL ANALYSIS METHODS

Continuous variables will be summarized using descriptive statistics including number of subjects (n), mean, standard deviation (SD), median, minimum, and maximum. Categorical variables will be summarized using frequencies and percentages. Percentages will be calculated using the total number of subjects in each treatment group for each applicable population and/or subpopulation, unless otherwise noted.

Number of subjects, minimums, and maximums will be calculated to the same number of decimal places as the source data. Means, standard deviations and quartiles will be calculated to one more decimal place than the source data. Percentages will be calculated to one decimal place. Zero count cells will be displayed as “0” with percentage of (0%). Unless otherwise noted, summaries will be performed by the treatment group (Placebo and RSLV-132 10 mg/kg).

If statistical tests are performed, the tests will be done at the two-sided, 5% significance level to compare Placebo vs. RSLV-132 10 mg/kg, unless otherwise specified. The point estimate and 95% confidence interval (CI) for the treatment differences may be displayed along with the p-value for the treatment comparison. P-values will be presented to three decimal places. P-values < 0.0005 will be presented as < 0.001. P-values greater than 0.999 will be presented as > 0.999.

In the absence of any predefined hypotheses in this study, the general strategy of the analysis will be to examine the data summaries for any trends amongst the treatment groups. No formal hypothesis testing will be carried out. P-values obtained from statistical testing of the analyses will be used for descriptive purposes only.

All data collected in the clinical database will be included in the data listings, as appropriate. Subjects who were randomized and never treated will be accounted for in the data listings.

6. SUBJECT DISPOSITION

6.1. Enrollment and Disposition of Subjects

Subjects' enrollment and disposition will be summarized by treatment group on two different analysis sets. The reasons for discontinuation will be listed in the order as they appear on the electronic case report form (eCRF).

Summary based on the ITT analysis set will include all randomized subjects and will be summarize for the following. The percentages will be calculated based on the number of subjects randomized in each of the treatment group.

- Number and percentage of subjects randomized
- Number and percentage of subjects randomized and discontinued prior to treatment
- The reason for discontinuation prior to treatment

Summary based on the FAS will include all randomized and treated subjects and will be summarize for the following. The percentages will be calculated based on the number of subjects randomized and treated in each of the treatment group.

- Number and percentage of subjects randomized and treated (Placebo or RSLV-132 10 mg/kg)
- Number and percentage of subjects randomized and treated who completed the study
- Number and percentage of subjects randomized and treated who discontinued from the study
- The reasons for study discontinuation
- Number and percentage of randomized and treated subjects included in each analysis set

6.2. Extent of Exposure

RSLV-132 or Placebo will be administered intravenously at 10 mg/kg at baseline, then weekly for two weeks and then once every 2 weeks for the next 20 weeks (13 administrations) to subjects with SLE.

Total duration of study drug dosing (Days), total number of infusions, total duration of infusion (Hours), total volume infused (mL) and total duration of study drug exposure will be summarized by treatment group on SAS. The number and percentage subjects with overall

infusion status (completed, interrupted or terminated) during the treatment period and the reason for interrupted or terminated will be summarized by treatment group on SAS. The percentages will be calculated based on the number of subjects in each treatment group of the SAS.

Total duration of study drug dosing will be calculated as the total number of days from the first dose date to the last dose date plus 1 regardless of temporarily dose interruptions. Total number of infusions will be calculated as the sum from each infusion segment (if the infusion was interrupted and then started again). Total duration of infusion in hours will be calculated as the total minutes from each infusion segment (if the infusion was interrupted and then started again) start time to end time.

Overall infusion completed is defined as a subject without any infusion interruptions or terminations during the study.

Total duration of study drug exposure (Days) is defined as the sum of (study Day 1 to the last visit date plus 1).

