## **5 INVESTIGATIONAL PLAN**

### **5.1 Overall Study Design and Plan**

This is a multi-center, double-blind, placebo-controlled study of approximately fifty subjects with SLE. Potential subjects will be screened to assess their eligibility to enter the study within twenty-eight days prior to study entry (i.e., prior to Baseline visit).

Subjects will be evaluated during screening for evidence of active, evaluable cutaneous manifestations of SLE which will be measured by the investigator using the CLASI score and documented using photography. The photographs will be adjudicated by a dermatologist with expertise in the use of the CLASI tool in SLE clinical trials in order to confirm the subject meets the CLASI entry criteria.

Following Baseline evaluations on Day 1, subjects will receive their first intravenous infusion of RSLV-132. Subjects will return to the research unit for additional visits as described in Appendix A.

The subjects will be randomized 2:1 (active:placebo) to receive IV administrations of 10 mg/kg of study drug or placebo as follows on days:

- 1, 8, 15, 29, 43, 57, 71, 85, 99, 113, 127, 141, and 155

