2.3.2. Treatment Groups and Dosing

Following Baseline evaluations on Day 1, randomized subjects will receive their first infusion of RSLV-132 or Placebo. RSLV-132 or Placebo will be administered intravenously at 10 mg/kg at baseline, then weekly for two weeks and then once every 2 weeks for the next 20 weeks (13 administrations) to subjects with SLE.

RSLV-132 shall be prepared for each subject from individual stock vials provided by Sponsor. Details of dilution, dose preparation, and administration instructions will be provided in the Study Drug Reference Manual. The dose for each individual shall be based on the subject's baseline body weight.

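### SAP 6.2 counts infusion segments rather than doses, so each restart adds one and the summarized count cannot be compared with the planned 13

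*SAP*

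**What the plan says.** SAP 6.2 opens with the schedule: one administration at baseline, "then weekly for two weeks and then once every 2 weeks for the next 20 weeks (13 administrations) to subjects with SLE". SAP 2.3.2 says the same, and Protocol 5.1 lists the dosing days as "1, 8, 15, 29, 43, 57, 71, 85, 99, 113, 127, 141, and 155". The primary objective in both documents (Protocol 4.1, SAP 2.1.1) is likewise framed as the effect of 13 infusions.

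SAP 6.2 then defines the exposure variables, all summarized by treatment group on the safety analysis set:

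- **Number of infusions:** "Total number of infusions will be calculated as the sum from each infusion segment (if the infusion was interrupted and then started again").
- **Infusion time:** "Total duration of infusion in hours will be calculated as the total minutes from each infusion segment", with the same remark about interrupted and resumed infusions.
- **Dosing duration:** counted "from the first dose date to the last dose date plus 1 regardless of temporarily dose interruptions".
- **Exposure duration:** "Total duration of study drug exposure (Days) is defined as the sum of (study Day 1 to the last visit date plus 1").
- **Infusion status:** completed, interrupted or terminated, with reasons. "Overall infusion completed is defined as a subject without any infusion interruptions or terminations during the study".
- **Total volume infused**, with no derivation rule and no planned value to compare it with.

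The SAP gives no other definition of the infusion count. It specifies no summary of missed doses, of doses received out of 13, or of percentage of planned dose.

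**The concern.** Adding up segments is right for time, because minutes are additive. It is wrong for a count of doses, because splitting one dose into two segments does not make it two doses. The two definitions stand next to each other in SAP 6.2 and share the segment wording.

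A reader of the exposure table will naturally set the number of infusions against 13. Under the rule as written that comparison fails in two ways. The count can exceed the number of scheduled doses, and a restart can cancel a missed dose. Of the summaries defined in SAP 6.2, this count is the one that would answer how many of the 13 planned doses were given, so an error in it is not corrected elsewhere in the section.

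**Working it through.** **Inputs from the documents**

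- Schedule: 1 at baseline + 2 weekly + 20/2 two-weekly = 1 + 2 + 10 = 13. Protocol 5.1 lists 13 dosing days, the last being Day 155. The plan's own figure reproduces exactly.
- Counting rule: sum over segments (SAP 6.2).
- Restart rate and missed-dose rate: neither is given. Values below are assumptions.

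**Per-subject count**

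Let D be the doses administered and R the number of restarts. Each restart creates one extra segment. An infusion stopped and not resumed creates none.

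- Segment rule: count = D + R
- Dose rule: count = D

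| D | R | Segment rule | Dose rule |
|---|---|---|---|
| 13 | 0 | 13 | 13 |
| 13 | 1 | 14 | 13 |
| 12 | 1 | 13 | 12 |
| 11 | 2 | 13 | 11 |

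Rows 1, 3 and 4 give the same segment count from 13, 12 and 11 doses. Each restart adds 1/13 = 7.7% of the planned number.

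**Group mean, fully dosed subjects**

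If a proportion q of infusions is restarted once, the mean excess is 13 × q:

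- q = 1%: 13 × 0.01 = 0.13 (mean count 13.13)
- q = 3%: 13 × 0.03 = 0.39 (13.39)
- q = 5%: 13 × 0.05 = 0.65 (13.65)

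**Group mean with missed doses**

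If a proportion m of doses is also missed, the mean segment count is 13 × (1 − m) × (1 + q). With m = 5% the true mean is 13 × 0.95 = 12.35 doses. The segment rule reports:

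- q = 2%: 12.35 × 1.02 = 12.60
- q = 5%: 12.35 × 1.05 = 12.97
- q = 10%: 12.35 × 1.10 = 13.59

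So at m = 5% and q = 5% the table would show a mean close to 13 although one dose in twenty was not given.

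**Do the other summaries in SAP 6.2 correct this?**

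- Dosing duration depends only on the first and last dose dates. A subject dosed on Days 1 and 155 has 155 − 1 + 1 = 155 days whatever was missed in between.
- Exposure duration runs to the last visit and does not respond to missed doses.
- Infusion status flags an interruption but not a missed dose.
- Volume depends on body weight (SAP 2.3.2), and two vial strengths were used (Protocol 7.1). With no planned volume stated, a group mean volume does not show how many doses were given.

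**The case against.** The best defense is that the sentence may simply have picked up the wording of the duration rule, with one count per dose intended. That is plausible, but the SAP does not say so, and a programmer will code what is written.

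The second defense is that little depends on the count, and this stands. The full analysis set requires only one dose (SAP 3.1.2), no per-protocol set or compliance threshold is defined, adverse event rates use the first-dose and last-visit dates (SAP 10.1.2), and no formal hypothesis testing is planned.

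A reader might draw three stronger conclusions that the documents do not support:

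- **That missed doses would be concealed.** Only the summary count is affected. A subject with 12 doses and one restart would not be classed as completed in the infusion status summary. Volume is reported, collected deviations are listed (SAP 6.3), and collected data go into listings (SAP 5). The underlying record is the per-dose date, rate and start and stop times (Protocol 8.4), with the pharmacist's dispensing record (Protocol 8.5). These may reveal a missed dose or an interruption for an individual subject.
- **That exposure is inflated in the active arm only.** Placebo is also infused and can also be interrupted and restarted. The excess follows restarts in each arm. The documents give no restart rates, and the summaries of the two earlier studies (Protocol 3.4.1 and 3.4.2) mention no infusion reactions.
- **That every interruption inflates the count, or that a known share of subjects would exceed 13.** Only a restart adds a segment. The share above 13 depends on the restart rate and on whether restarts cluster within subjects; the documents inform neither.

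**Conclusion.** The point holds as a defect in one definition. As written, SAP 6.2 makes the number of infusions equal to doses plus restarts, which conflicts with the documents' own use of 13 infusions for 13 scheduled doses. The summarized count can exceed 13, can equal 13 when doses were missed, and is overstated most in whichever arm has more restarts.

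The size per restart is exact: one infusion, or 7.7% of the planned 13. The group-level size is conditional. A mean excess of 0.13, 0.39 or 0.65 in fully dosed subjects rests on assumed restart rates of 1%, 3% and 5% with one restart per affected infusion. These means do not require restarts to be independent within a subject.

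The importance is minor. It is a misreported figure in a descriptive table and changes no efficacy result or adverse event rate. It is nonetheless a stated rule that yields a wrong number, not merely a missing detail.

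**What to change.** In SAP 6.2:

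1. Define the total number of infusions as the number of scheduled dosing visits at which an infusion of study drug (RSLV-132 or placebo) was started, with range 0 to 13.
2. Keep the sum over segments for total infusion duration only.
3. Report the number of restarts separately, next to the existing summary of interrupted and terminated infusions.

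The count then cannot exceed 13, and every missed dose lowers it by one. An infusion started and then terminated still counts as one, so the count should be read together with the infusion status summary, which already identifies terminations.

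The cost is about one sentence in the SAP and a small programming change for the count, plus a line in the table for restarts. No new data are needed, because dates and start and stop times are recorded for each dose (Protocol 8.4). The SAP revision history (SAP 12) shows that the infusion duration formula in the same section has already had a correction of this kind.
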